1.1 Trial registration number: ISRCTN15380317

This SAP is based on protocol version 7.0 (date 16/08/2022)

1.2 SAP revision history

Protocol version	Updated SAP version no.	Section number changed	List of changes from previous version/protocol	Author of change	Date
7.0	0.1			[name]	17/10/2022
7.0	0.2			[name]	04/11/2022
7.0	0.3			[name]	22/11/2022
7.0	0.4			[name]	01/12/2022
7.0	0.5	6.6 & 6.9	Minor change suggestion by independent statistician: Specify complete case data as primary analysis and multiply imputed data as sensitivity analysis.	[name]	12/04/2023
7.0	0.6	6.6 & 6.9	Change suggested by independent statistician incorporated. Other relevant track changes and comments removed.	[name]	13/04/2023
7.0	0.7	Sections throughout	Incorporate comments by senior statistician (TH) and chief investigator	[name]	20/04/2023
7.0	0.8	Sections throughout	Incorporate comments by chief investigator	[name]	24/04/2023
7.0	1.0	Sections throughout	Final comments from senior statistician (TH) incorporated.	[name]	27/04/2023

*If the SAP has been published, indicate which version.

1.4 Timing of SAP revisions in relation to unblinding of data/results

No members of the writing committee have, or will have, access to data before the statistical analysis plan is signed off.

1.5 Remit of SAP

The current Statistical Analysis Plan (SAP) outlines detail of statistical analyses and tables to be reported within the principal paper(s) of the IBD-BOOST OPTIMISE non-randomised intervention study (IBD-BOOST WP2c). It details the sample size justification and intended statistical analyses of primary and secondary study aims and outcomes, subgroup analyses, and sensitivity analyses. Unplanned, post hoc analyses will be transparently reported in the study manuscript.

AE	Adverse Events
BCC	Barts Cancer Research UK Centre
ССИК	Crohn's & Colitis UK (registered charity supporting people with IBD)
CD	Crohn's disease
CRF	Case Report Form
CI	Chief Investigator
CV	Curriculum Vitae
FI	Faecal Incontinence
GCP	Good Clinical Practice
GDPR	General Data Protection Regulation
GP	General Practitioner
HRA	Health Research Authority
IBD	Inflammatory Bowel Disease
IRAS	Integrate Research Application System
KCL	King's College London
LNWH	London Northwest Healthcare NHS Trust
NHS	National Health Service
NICE	National Institute for Clinical Excellence
NIHR	National Institute for Health Research
NRES	National Research Ethics Service
PCTU	Pragmatic Clinical Trials Unit (Queen Mary, University of London)
PCfAR	Programme Grant for Applied Research
PI	Principal Investigator
PIS	Patient Information Sheet
PMG	Programme Management Group
PSC	Programme Steering Committee
PPI	Public and Patient Involvement
QMUL	Queen Mary's University of London
RCT	Randomised Control Trial
REC	Research Ethics Committee
SAEs	Serious Adverse Events
SAP	Statistical Analysis Plan
SoA	Statement of Activities
SoE	Schedule of Events
UC	Ulcerative Colitis

Abbreviations/Glossary of terms

2. Introduction

Inflammatory Bowel Disease (IBD) affects 300,000 people in the UK

(https://www.crohnsandcolitis.org.uk/about-inflammatory-bowel-disease), causing unpredictable bouts of gut inflammation, with acute illness, diarrhoea, and pain. In remission, many people with IBD live with fatigue, chronic pain, and bowel urgency/incontinence (1). There is no current cure for IBD, which usually starts in childhood or as a young adult. Most previous IBD research has focused on controlling inflammation. However, many people report continuing IBD-related fatigue (41%), abdominal pain (62%) and difficulty with continence (up to 75%) even when IBD is in remission (1-3). These symptoms limit peoples' quality of life and ability to work and socialise. Patients feel these symptoms are not taken seriously by health professionals and report that little help is given (4-6). However, the James Lind Alliance IBD research priority-setting consensus put fatigue, pain, and continence in the top 10 issues that IBD patients and clinicians want to be addressed by research (7).

2.1 The IBD-BOOST programme of research

The current study forms stage three of IBD-BOOST – a National Institute of Health Research (NIHR) Programme Grant for Applied Research (PGfAR) funded programme. The overall aim of the Programme Grant is to improve the quality of life of people with IBD by reducing the burden of IBDrelated fatigue, pain, and urgency/incontinence. The current Statistical Analysis Plan is for stage 3 of the programme, a non-randomised intervention study to test a checklist and algorithm for identifying and managing potential medical causes of these IBD-related symptoms.

Stage 1 of the programme involved focus groups and interviews with people with IBD and IBD nurses to inform the development of the checklist and algorithm under investigation in this study.

Stage 2 of the programme involves a large cross-sectional survey of people with IBD to investigate the inter-relationships of these IBD-related symptoms and the proportions wanting support to manage these symptoms. Survey participants who consent to be contacted for further stages of our research, and who attend one of our clinical sites for their routine IBD care, will be invited to participate in the Optimise Study (this stage) and then, if eligible, will later be invited to participate in the RCT.

Stage 3 (this project) of the programme comprises a non-randomised intervention study to test a checklist and clinical management algorithm which we have developed within this programme for identifying and managing the most common medical causes of these IBD-related symptoms. We will then address any medical abnormalities detected.

Stage 4 Participants who have no medical causes identified by the checklist and algorithm, or who have abnormalities and complete this medical optimisation but have continuing symptoms after medical optimisation will then be invited to take part in an RCT of online self-management. The RCT will also be offered to eligible people declining participation in the present study, or who consent to the present study and complete the checklist but who subsequently decline any suggested medical test or intervention.

1.2 Rationale

Symptoms of fatigue, pain, and urgency/incontinence have a major impact on quality of life in people with IBD but have been largely ignored by clinicians and researchers. Our programme,

shaped by the concerns of our patient and clinician stakeholders, focuses on a supported online selfmanagement intervention for these symptoms. The current checklist and algorithm stage will help identify participants who will be suitable for a self-management intervention and ensure that anyone displaying "red-flag" symptoms (indicating an urgent or serious medical issue) is identified for prompt treatment. It is currently unclear how useful it is to investigate these symptoms and whether symptoms will respond to correcting biomedical abnormalities.

1.3 The need for research

It is currently unclear how best to manage these common symptoms of fatigue, pain, and urgency/incontinence in people with inflammatory bowel disease. Many patients do not report these symptoms at all, or if they do are offered little beyond investigation and treatment of active disease. We have found in previous work that many patients do not receive what are considered "standard care" investigations or management for these symptoms (8). Our previous systematic literature reviews (9-12) have identified many potentially reversible causes for these symptoms. Many of these, particularly the psycho-social elements, will be addressed in our online selfmanagement programme which follows on from the current proposal within our programme grant. However, there are also "medical" causes (such as anaemia as a cause of fatigue), which could be addressed before patients enter a self-management programme. However, during extensive consultation with expert clinicians during development of the current checklist and algorithm, there is genuine equipoise over whether patients need these medical causes addressing, whether it is likely to make any difference to symptoms, or whether they should be able to directly access online self-management.

1.4 Development of the checklist and algorithm

Development work for this study has involved consulting a wide variety of gastroenterologists, IBD specialist nurses, patients and others. This work suggests that there is no current "standard of care" for investigating and treating these symptoms. Some clinics do very little while others conduct many different tests, with little consideration of costs or inconvenience to patients. Over an extensive series of interviews and group activities with stakeholders, there is now consensus on the contents of an algorithm for investigating and managing symptoms of fatigue pain and urgency/incontinence, with an accompanying preliminary self-completed checklist. During this development we have focussed on the common evidence-based causes (from our systematic reviews above) and interventions for our three symptoms (fatigue, pain, urgency), which consultees felt were also feasible for implementation in routine clinical practice. We have tried to achieve a balance between feasibility, costs and completeness. There were many other candidate tests, which were either not evidence-based or that patients and clinicians felt were too onerous to be part of routine clinical care for all patients with these symptoms.

3. Background and trial design

Study objectives	 To determine the proportion of participating IBD patients with fatigue, pain, and/or faecal urgency/incontinence who have pathophysiological contributors that are potentially medically treatable. To describe changes in symptoms three months after initiating algorithm-led management amongst patients with IBD-related symptoms and potentially reversible medical causes. To evaluate changes in health-related quality of life amongst patients with IBD-related symptoms starting algorithm-led management. To ascertain the feasibility of implementing IBD symptom checklist and algorithm in clinical practice. To determine what resources, such as costs, are incurred by the NHS during implementation of the algorithm.
	5. To qualitatively evaluate the experience and suggestions of
Study design	nurses implementing the algorithm. Multi-site, non-randomised, intervention study
Setting	Four NHS Trusts:
	 Barts Health NHS Trust (Royal London Hospital) Dorset County Hospital NHS Foundation Trust (Dorset County Hospital) London Northwest University Healthcare NHS Trust (St Mark's Hospital & Northwick Park Hospital)
	 St Helens and Knowsley Teaching Hospitals NHS Trust (Whiston Hospital or St Helen's Hospital)
Participants	Adults with IBD who have completed the IBD-BOOST survey at stage 2 of the Programme Grant and have indicated on that survey that they would like further support for their symptoms Number of participants 200
	 Inclusion criteria Diagnosis of IBD (including patients with an ileo-anal pouch or stoma) 18 years and over Lives in UK and attends one of the IBD-BOOST clinical sites for routine IBD care Has completed the IBD-BOOST survey (stage 2 of Programme Grant) and indicated that they would like further support to help manage their symptoms Ability to give informed consent and sufficient command of English to understand study documents and procedures will be assumed from response to the previous survey

	Exclusion criteria		
	Under 18 years		
Interventions	Study participants will complete a self-report symptom checklist and provide a stool sample. A healthcare professional from their clinical site will review checklist responses using an agreed algorithm and offer to initiate additional tests or clinical management as indicated by the algorithm. There is no control group in this non-randomised, intervention study.		
Primary outcome	Feasibility outcomes		
measure(s)	 Proportion of consenting participants who: (i) completed the symptom checklist (ii) returned the postal faecal calprotectin test Proportion of participants for whom, after returning both the symptom checklist and faecal calprotectin test, no algorithm-informed action was indicated (and thus could progress to the RCT) Proportion of participants for whom algorithm-informed action was indicated where the clinical team completed and returned the CRF (to indicate the actions they planned) Of participants where algorithm-informed actions were indicated, the proportion who completed outcome measures at three months (i.e., attrition rates). Number and proportion of participants consenting to receive the algorithm-informed intervention but then discontinuing (with reasons if possible). 		
	 Clinical outcomes The proportion of patients with any of the following, detected using the self-report symptom checklist, faecal calprotectin test, or by the nurse/clinician following the algorithm: "Red flags" on the self-report symptom checklist that require investigation (as a single binary indicator variable). Active disease (defined as faecal calprotectin ≥200 and/or IBD control score ≤13). Participants for whom interventions for fatigue are advised or prescribed (based on detected blood test abnormalities). Participants for whom interventions for pain are advised or prescribed (based on irritable bowel syndrome or functional dyspepsia, as diagnosed from responses on checklist). Participants for whom interventions for faecal urgency are advised or prescribed (based on the detection of untreated loose stool). 		

4. Outcome measures

As the IBD-BOOST Optimise study had to be adapted due to covid-19, with reduction of planned sample size from 500 to 200, the main focus of analysis will be on feasibility outcomes:

- Proportion of consenting participants who:
 (iii) completed the symptom checklist
 (iv) returned the postal faecal calprotectin test
- Proportion of participants for whom, after returning both the symptom checklist and faecal calprotectin test, no algorithm-informed action was indicated (and thus could progress to the RCT)
- Proportion of participants for whom algorithm-informed action was indicated where the clinical team completed and returned the CRF (to indicate the actions they planned)
- Of participants where algorithm-informed actions were indicated, the proportion who completed outcome measures at three months (i.e., attrition rates).
- Number and proportion of participants consenting to receive the algorithm-informed intervention but then discontinuing (with reasons if possible). Discontinuing will be defined as actively notifying study personnel of withdrawal or failing to respond to the OPTIMISE questionnaire at three months if it was indicated.

4.1 Primary clinical outcome measures (upon administration of the self-report symptom checklist and faecal calprotectin test, before delivery of algorithm-informed intervention(s)):

The proportion of patients with any of the following, detected using the self-report checklist, faecal calprotectin test, or by the nurse/clinician after implementing the algorithm:

- "Red flags" on the self-report symptom checklist that require investigation (as a single binary indicator variable).
- Active disease (defined as faecal calprotectin \geq 200 and/or IBD control score \leq 13).
- Participants for whom interventions for fatigue are advised or prescribed (based on detected blood test abnormalities).
- Participants for whom interventions for pain are advised or prescribed (based on irritable bowel syndrome or functional dyspepsia, as diagnosed from responses on checklist).
- Participants for whom interventions for faecal urgency are advised or prescribed (based on the detection of untreated loose stool).

4.2 Secondary clinical outcomes

Prior to algorithm-informed intervention(s):

- (i) The proportion of participants for whom clinical intervention was indicated by the algorithm.
- (ii) The proportion of participants who declined a suggested clinical intervention by the algorithm.

Prior to and following algorithm-informed intervention:

(iii) The following outcome measures will be obtained from the IBD-BOOST stage 2 survey dataset for the prior time point. Outcome assessment will be repeated at three months

after return of the self-report symptom checklist and algorithm for patients who undergo algorithm-informed intervention(s):

- PROMIS Short Form v1.0 Fatigue 4a [Four-item validated scale to measure fatigue (14)];
- PROMIS Scale v1.0 Pain Intensity 3a [Three-item validated scale to measure pain (14)];
- PROMIS Scale v1.0 Gastrointestinal Bowel Incontinence 4a [Four-item validated scale to measure bowel control (15)];
- IBD-Control score [Eight-item self-reported score to measure disease control from the patient's perspective (13)], and;
- EQ-5D-5L (Quality of Life measurement) [Five-item standardised measure of health (16)].
- (iv) The economic cost of implementing the algorithm (i.e., cost of clinical tests, intervention(s), and the time required the nurse/clinician to implement algorithm)
 [Health Economics objective that will be detailed in HEAP and is not being analysed as part of the statistical analysis].

5. Sample size and randomisation

5.1 Initial sample size justification (500 participants)

From the prevalence of symptoms in IBD patients, it is anticipated that at least 50% of 6,300 predicted respondents to the survey (stage 2) will report one or more symptoms of fatigue, pain, or urgency/faecal incontinence (n=3,150 symptomatic individuals). Of symptomatic participants, it is anticipated that approximately one-third will express an interest in further management for these symptoms and attend one of our clinical sites for routine IBD care (~1,000 individuals available as potential recruits for the present study). Of ~1,000 potential recruits, it is anticipated that 50% (500 individuals) will consent to participate in the OPTIMISE study.

5.1a Revise sample size

Due to the impact of the COVID-19 pandemic on study recruitment, with only 4 of the anticipated 20 NHS sites ever opening, it was necessary (with Steering Group, funder, and ethical approval) to reduce the target sample size from 500 participants to 200 participants and convert this to a feasibility study with the focus on feasibility outcomes (see above). With a sample size of 200 participants, the width of the 95% confidence interval (CI) for the proportion of participants with pathophysiological contributors that are potentially medically treatable will be at most 13.9% (normal approximation CI).

5.2 Randomisation procedure

As this is a non-randomised, intervention study, no randomisation procedure is required.

5.3 Blinding of research personnel

The chief investigator, senior statistician, and trial statistician are blinded – that is, did/do/will not access any study data prior to statistical analysis.

6. Analysis methods

6.1 Baseline characteristics

Baseline demographic characteristics and clinical characteristics obtained when conducting the survey (**stage two**) will be presented using descriptive statistics. Categorical variables will be presented as absolute frequencies and percentages. Continuous variables will be presented as means and standard deviations or as medians and inter-quartile ranges, depending on the data distribution. Draft tables are presented in the appendix.

6.2 Data completeness

The number and percentage of study participants with missing data for each variable will be presented.

6.3 Information for flow diagram

The flow of participants through the following phases of the OPTIMISE study will be reported using a flow-diagram modified for the reporting of evaluations of non-randomised, intervention studies:(17)

- Enrolment: the number of survey (stage two) respondents who (i) are eligible to participate in the OPTIMISE study, (ii) express an interest in receiving further management for their IBD-related symptoms and thus were invited to participate, and (iii) consented and are enrolled in the OPTIMISE study.
- (ii) Assignment: the number of study participants who (i) receive the self-report symptom checklist, (ii) complete the self-report symptom checklist, (iii) are administered the faecal calprotectin test, and (iv) return the faecal calprotectin test.
- (iii) Allocation & intervention exposure: the numbers of participants (i) for whom the OPTIMISE algorithm indicates that no further action is required (ii) for whom a red flag is identified and no further OPTIMISE intervention is permitted (iii) who are (iv) assigned to (each) intervention, as informed by the OPTIMISE algorithm, and (v) receive (each) intervention.
- (iv) Follow-up: the number of participants receiving algorithm-informed management who do and do not complete study follow-up (three months after completing the self-report symptom checklist at baseline).
- Analysis: the number of participants included in or excluded from the analyses of primary outcome, outcomes at three-months, and change in patient-reported outcome measures amongst participants who receive algorithm-informed interventions.

A template flow chart is presented in Appendix 1.

6.4 Adherence to treatment

Adherence to algorithm-informed intervention will not be measured in the IBD-BOOST OPTIMISE study.

6.5 General analysis principles

Study participants who express desire for support with IBD-related symptoms and receive the selfreport symptom checklist will be included in descriptive baseline analyses. For study participants who receive algorithm-informed intervention(s), the effect size (e.g., mean change in symptom severity scores) will be estimated. A two-sided p-value and 5% alpha level will be used to declare

statistical significance. However, the focus of this analysis is descriptive. Ninety-five percent confidence intervals (95%Cls) will be reported unless stated otherwise.

6.6 Analysis of the primary clinical outcomes

To fulfil the primary study objective, the proportion of study participants with (i) red flags, (ii) active IBD disease, (iii) blood test abnormalities (in participants with fatigue), (iv) irritable bowel syndrome or functional dyspepsia (in participants with pain), and (v) untreated loose stool (in participants with urgency) will be estimated. We will construct 95%CIs around proportion estimates using Wilson's Score Interval to minimize the loss of coverage that typically occurs with normal approximations of the Wald Interval. Complete case analyses (ignoring missing data) will be performed for primary outcomes.

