6.11 Sensitivity analyses

To assess the extent to which study results are affected by missing data, a sensitivity analysis will be performed on imputed data for primary clinical outcomes (23). The proportion of missing values for each variable will be assessed using numerical and graphical summaries. Univariable associations between missing values of each variable and observed values of other variables will be examined to understand how reliably a missing value might be imputed (18). This will be performed by constructing separate logistic regression models after creating a binary indicator variable for each variable with missing values coded as "1" and non-missing values coded as "0". The most applicable missing data mechanism will be informed by clinical knowledge of independent and dependent variables, reasons for missingness, and relationships between missingness and the observed values of collected variables.

Multivariate Imputation using Chained Equations (MICE) will be used to impute missing data under the expectation that both independent and dependent variables will have missing values and the data will not be monotonic missing (19). MICE replaces missing values with a random sample of plausible, imputed values drawn from their predictive distribution (20). First, an 'imputation' step will be performed, which involves constructing an imputation model that replaces missing data with one set of plausible values. Assuming that missing data are 'Missing At Random', the imputation model will specify a conditional distribution for missing values of each variable given the observed values of other variables. This imputation model will repeatedly replace missing values with a random sample of plausible values, creating a completed dataset with each imputation. The number of imputations (and thus completed datasets generated) will mirror the proportion of participants with at least one missing value. For example, 25 complete datasets will be generated if 25% of study participants have at least one missing value (21).

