6. EQ-5D-5L

Each of the five dimensions, mobility, self-care, usual activities, pain/discomfort, and anxiety/depression, comprising the EQ-5D descriptive system is divided into five levels of perceived problems:

LEVEL 1: indicating no problem LEVEL 2: indicating slight problems LEVEL 3: indicating moderate problems LEVEL 4: indicating severe problems LEVEL 5: indicating unable to/extreme problems A unique health state is defined by combining one level from each of the five dimensions. Levels 1-5 are coded as 1-5, respectively, and combining a level for each dimension gives a five-digit health state. These health states are then converted to an indexed value using the EQ-VT for England. The Index value set calculators are found on the Euroqol website and have been saved in the BOOST BCC folder as a Stata do file (Z:\STATISTICIANS\IBD-BOOST\EQ-5D-

Study IBD-BOOST OPTIMISE Document version 1.0

5L index value calculator). The EQ-VAS score is continuous and ranges from 1-100, with 100 indicating "the best health you can imagine" and 0 indicating "the worst health you can imagine." This score shows the patient's perceived overall health and requires no further derivation.

Requirements Specification Document Primary Clinical Outcomes

Clinical outcome – Abnormalities detected on blood test in people with fatigue

- Optimisation CRF: **130. fatiguenew D1.1**. Were new tests ordered for causes of fatigue? If that answer is YES and then **198. ftginterven E1.1.** Were interventions for fatigue advised or prescribed? If that is YES that means there was something abnormal.

Clinical outcome – Irritable Bowel Syndrome or functional dyspepsia indicated in people with pain (by responses on checklist)

- Optimisation CRF: **266. paininterven F1.1.** Were interventions for pain advised or prescribed? If that is a YES that means they had IBS or functional dyspepsia pain. We use a scoring system for these which I can send if helpful using the answers on the checklist. Redcap does this automatically. You can see this on the RSD section 3.7 questions 4 and 5.

Clinical outcome - Untreated loose stool detected in people with faecal urgency.

- Optimisation CRF - **280. urgencyadv G1.1. Were interventions for urgency advised or prescribed?** If this is a YES it means they had untreated urgency.

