Appendix 3: Descriptive analysis tables

Table 1: Number and percentage of OPTIMISE study participants by site

	N approached	Response rate (%)
Site		
Barts Health NHS Trust (Royal London Hospital)		
Dorset County Hospital NHS Foundation Trust (Dorset County Hospital)		
London Northwest University Hospital NHS Trust		
(St Mark's Hospital or Northwick Park Hospital)		
St Helens and Knowsley Teaching Hospitals NHS Trust		
(Whiston Hospital or St Helen's Hospital)		

TOTAL

PCTU

		Algorithm-informed	Algorithm-informed
Characteristic	Total	intervention(s) indicated	intervention(s) not indicated
Gender, n (%)			
Male			
Female			
Prefer to self-define			
Prefer not to say			
Missing			
Age (years), mean (sd)			
Ethnicity, n (%)			
Asian			
Black			
Mixed			
Other			
White			
Prefer not to say			
Missing			
Employment, n (%)			
Full time			
Part time			
Student			
Retired			
Unemployed			
Self-employed			
Homemaker			
Unemployed due to			
illness/disability			
Missing			
Education, n (%)			
No formal education			
Secondary school			
Sixth form			
Further education			
Higher education			
Missing			
Relationship Status, n (%)			
Married/ civil partnership			
Living with partner			
Widowed			
Divorced/separated			
Single			
With partner, not living			
together			
PCTU_TEM_ST_02	_	:	Study IBD-BOOST OPTIMISE

Table 2. Demographic and lifestyle characteristics at baseline

PCTU_TEM_ST_02 Statistical Analysis Plan template v3.0

Missing Smoker, n (%) Never Ex Current Missing Alcohol (units/week) – mean (sd) Missing

Table 3: Clinical characteristics at baseline

		Algorithm-informed	Algorithm-informed
	Total	intervention(s)	intervention(s) not
Characteristic		indicated	indicated
BMI (kg/m ²) – mean (sd)			
Underweight, n(%)			
Healthy weight, n(%)			
Overweight, n(%)			
Missing			
Operation, n(%)			
Missing			
Stoma, n(%)			
Missing			
Pouch, n(%)			
Missing			
Fistula, n(%)			
Missing			
Biologic medication, n(%)			
Missing			
Non-biologic medications, n(%)			
Missing			
Mental health conditions, n(%)			
Missing			
Physical health conditions, n(%)			
Missing			
Pregnant, n(%)			
Missing			
Depression, n(%)			
None			
Mild			
Moderate			
Moderately severe			
Severe			
Missing			
Anxiety, n(%)			
None			
Mild			
Moderate			
Severe			
Missing			

Table 4: Number and percentage of participants with primary outcomes (complete case analysis)

Outcome	n (% of non-missing)
At least one red flag on self-report checklist	n (%)
Active disease*	n (%)

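### The fatigue, pain and urgency outcomes have no defined negative value; if the Optimisation CRF is completed only when an action is indicated, dropping blanks inflates all three proportions

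*SAP*

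**What the plan says.** - **Source of the outcomes.** Appendix 2 (Requirements Specification Document, Primary Clinical Outcomes) reads the fatigue outcome from CRF item D1.1 (new tests ordered) followed by E1.1 (intervention advised or prescribed). Pain comes from F1.1, and urgency from G1.1: "Were interventions for urgency advised or prescribed". In each case only the meaning of YES is given.
- **When the CRF is due.** One feasibility outcome (section 3 table and section 4) is: "Proportion of participants for whom algorithm-informed action was indicated where the clinical team completed and returned the CRF (to indicate the actions they planned". A separate feasibility outcome counts participants with no action indicated, who can move on to the RCT.
- **Red flags.** The flow diagram in section 6.3 has a group "for whom a red flag is identified and no further OPTIMISE intervention is permitted".
- **Missing data, primary analysis.** Section 6.6: "Complete case analyses (ignoring missing data) will be performed for primary outcomes". The column heading of Table 4 is "n (% of non-missing".
- **Missing data, sensitivity analysis.** Section 6.11: "a sensitivity analysis will be performed on imputed data for primary clinical outcomes". It uses chained equations under Missing At Random, with logistic models for binary variables. Table 10 lists all three intervention outcomes.
- **Denominator.** Section 6.6 restricts the three outcomes to participants with the matching symptom. Section 4.1 and Table 4 show no such restriction.

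**The concern.** A participant may return the checklist and stool test, have no action indicated, and so have no CRF. That participant is a true negative for all three outcomes, but in the dataset the items are blank. Nothing in the SAP separates a blank that means not applicable from a blank that means a due form was not returned. Read literally, section 6.6 and Table 4 remove these negatives, and section 6.11 treats them as unknown and imputes them.

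At stake is the first study objective, the proportion of participants with potentially treatable contributors. The reported figure could become a proportion among people who already had some action indicated, under a heading that suggests all participants. Red flags and active disease are not derived from these CRF items and are not affected.

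**Working it through.** **1. The plan's own figure.** Section 5.1a sets out to "reduce the target sample size from 500 participants to 200 participants" and says the 95% CI width "will be at most 13.9% (normal approximation CI". The Wald width at p = 0.5 is 2 × 1.96 × √(0.25/200) = 0.1386, or 13.9%, so it reproduces. The Wilson interval named in section 6.6 gives 13.7% at 100/200. The stated precision therefore takes all 200 participants as the denominator.

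**2. Formula.** Let N be the relevant denominator (all participants in Table 4, those with the symptom in section 6.6), x the number with the intervention, and q the share of N with no action and no CRF. With every due CRF returned:
- no-action coded No: x/N
- complete case: x/(N(1 − q))
- ratio: 1/(1 − q)

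The ratio depends on q alone, so it applies to either denominator, but q itself may differ between them.

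**3. Numbers.** Neither q nor x is in the SAP. Assume N = 200 (the Table 4 reading) and x = 40. With no-action coded No, the result is 40/200 = 20.0% (Wilson 15.0 to 26.1).

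| Assumed q | CRFs held | % of non-missing (Wilson 95% CI) | Factor | Maximum Wald width |
|---|---|---|---|---|
| 10% | 180 | 40/180 = 22.2% (16.8 to 28.8) | 1.11 | 14.6% |
| 30% | 140 | 40/140 = 28.6% (21.7 to 36.5) | 1.43 | 16.6% |
| 50% | 100 | 40/100 = 40.0% (30.9 to 49.8) | 2.00 | 19.6% |

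**4. Imputation.** If blanks are filled at the observed rate, the expected number of interventions given to people who had none indicated is 60 × 40/140 = 17.1 at q = 30%, and 100 × 40/100 = 40 at q = 50%. The imputed proportion then equals the complete-case one.

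A better imputation model does less harm. A simulation used 200 participants, about half with an action indicated, and one covariate related to both action and intervention. The logistic imputation model was fitted to CRF holders only (300 runs, 20 imputations each). The mean results were:
- no-action coded No: 21.3%
- complete case: 42.5%
- multiple imputation: 36.5%, about 31 surplus interventions per 200

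The bias shrinks but stays, because the model has no observed outcome from the group it is filling in.

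**5. The fatigue item.** The rule reads E1.1 after D1.1 = YES. It gives no value when D1.1 = NO, so this gap exists even where a CRF was completed.

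**The case against.** The strongest reply is that the decisive step is inferred. The SAP sets CRF return among participants with an action indicated as one feasibility denominator. It does not say that no CRF is opened for the others. The section 3 table has a healthcare professional reviewing checklist responses without restricting this to any subgroup, and a gate item such as D1.1 suits a form that also records NO. The form's completion rule is not in the document. This stands: the bias is conditional, and a reader might wrongly infer that the SAP shows treatable causes will be overstated.

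Second, the table above uses all 200 participants. Under the symptom denominators of section 6.6, a no-action participant without the symptom belongs outside the denominator, and only symptomatic participants with no action would be wrongly lost. That also stands. It limits q but does not remove the problem, and Table 4 shows no symptom restriction.

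Third, section 6.11 foresees auxiliary variables and a review of the reasons for missingness. A reader might infer that Tables 4 and 10 would agree on the same wrong figure. The simulation does not support that: 42.5% and 36.5% differ. Both remain well above 21.3%, however.

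Fourth, the analyses are descriptive and the study was refocused on feasibility. That lowers the consequences. It does not supply the missing rule.

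**Conclusion.** The SAP defines no negative value for three of its five primary clinical outcomes, and its missing-data rules do not separate a structural negative from a lost form. If participants with no action indicated have no CRF, the direction is certain: dropping true negatives can only raise a proportion. The inflation is up to 1/(1 − q): 1.11, 1.43 or 2.00 for assumed q of 10%, 30% or 50%. The actual size cannot be known from the document, and Missing At Random imputation lessens it at best.

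A reader might infer that only a CRF for every participant removes the bias. That is too strong. Coding no-action blanks as No at derivation also removes it, and under section 6.6 it vanishes if every no-action participant lacks the symptom. Conversely, universal CRFs alone are not quite enough for fatigue: D1.1 = NO must also be coded as No.

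**What to change.** Change Appendix 2, sections 6.6 and 6.11, and Tables 4 and 10:

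- **(a) No:** code the intervention-advised-or-prescribed outcome as No when checklist and calprotectin were both returned and no action was indicated for that symptom, and when D1.1 = NO.
- **(b) Missing:** code it missing when the checklist or calprotectin was not returned, or when an action was indicated and the CRF was not returned.
- **(c) Not assessed:** show red-flag participants routed out of the algorithm in their own row.
- **(d) Imputation:** impute category (b) only.
- **(e) Denominator and label:** use one stated denominator, all participants or those with the symptom, in section 6.6, Table 4 and Table 10. Label outcome (iii) as intervention advised, so that untested people are not reported as free of blood test abnormalities.

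If sites do complete a CRF for everyone, a sentence saying so and a value for D1.1 = NO settle the coding of negatives; (e) is still needed.

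The cost is one derivation rule and its code. No new data are needed, and the reported proportions may be lower.
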